#### 7.4 Adverse Events

The Investigator is responsible for ensuring that all staff involved in the study are familiar with the content of this section.

An AE is defined as any untoward medical occurrence in a subject administered a pharmaceutical product during the course of a clinical investigation. An AE can therefore be any unfavorable and unintended sign, symptom, or disease temporally associated with the use

23 February 2021 CONFIDENTIAL Page 39 of 60

b Serum.

c Serum phosphorus is performed separately from standard clinical laboratory tests at protocol-specified time points.

<sup>d FSH and serum pregnancy tests are performed on all females <60 years of age unless there is a documented method of sterilization, or FSH test confirms post-menopausal status.

e Plasma

Protocol Number: TEN-02-402

Edition No. 2

of an investigational product, whether or not thought to be related to the investigational product.

Patients will be monitored throughout the study for AEs, from Screening (Visit 1) through the end of the study. Medical events that occur before Screening (Visit 1) and are ongoing at Screening (Visit 1) should be recorded as medical history, not AEs. All AEs spontaneously reported by the patient or reported in response to the open question from the study personnel such as "Have you had any health problems since the previous visit?", or revealed by observation will be collected and recorded in the AE eCRF. When collecting AEs, the recording of diagnoses is preferred (when possible) to recording a list of signs and symptoms. In instances of well-recognized symptoms, they can be recorded as the commonly used diagnosis (e.g., fever, runny nose, and cough can be recorded as "flu"). However, if a diagnosis is known, but there are other signs or symptoms that are not generally part of the diagnosis, the diagnosis and each sign or symptom should be recorded separately.

Each AE must be followed until it is resolved or stabilized, or until all attempts to determine resolution of the AE are exhausted. All AEs that are ongoing at the end of study will be recorded as ongoing in the eCRF. The procedures specified in Section 7.4.7 are to be followed for reporting SAEs.

#### 7.4.1 Recording Adverse Events

Adverse events are to be recorded on the AE eCRF. Severity of an AE will be graded according to the following definitions:

- Mild: The patient experiences awareness of symptoms but these are easily tolerated or managed without specific treatment.
- Moderate: The patient experiences discomfort enough to cause interference with usual activity, and/or the condition requires specific treatment.
- Severe: The patient is incapacitated with inability to work or do usual activity, and/or the event requires significant treatment measures.

Action taken with study drug (Tenapanor or phosphate binder) due to AEs will be categorized as dose not changed, dose reduced, drug interrupted, drug withdrawn, or not applicable. Other actions taken due to AEs will be categorized as required concomitant medication, required concomitant procedure, discontinued from study, and/or other.

Event outcome at resolution or time of last follow-up will be recorded as not recovered/not resolved, recovered/resolved with sequelae, recovering/resolving, fatal, or unknown.

23 February 2021 CONFIDENTIAL Page 40 of 60

Protocol Number: TEN-02-402

Edition No. 2

#### 7.4.2 Assessment of Adverse Events

The relationship of an AE to the study drug (tenapanor or phosphate binder) should be determined by the Investigator according to the following criteria:

- Not related: The event is most likely produced by other factors such as the patient's
  clinical condition, intercurrent illness, or concomitant medications, and does not follow a
  known response pattern to the study drug, or the temporal relationship of the event to
  study drug administration makes a causal relationship unlikely.
- Possibly related: The event follows a reasonable temporal sequence from the time of drug administration and is possibly due to drug administration and cannot be reasonably explained by other factors such as the patient's clinical condition, intercurrent illness, or concomitant medications.
- Related: The event follows a reasonable temporal sequence from the time of drug
  administration, and/or follows a known response pattern to the study drug, and cannot be
  reasonably explained by other factors such as the patient's clinical condition, intercurrent
  illness, or concomitant medications.

## 7.4.3 Following Adverse Events

All (both serious and non-serious) AEs must be followed until they are resolved or stabilized, the condition becomes chronic in nature, all attempts to determine resolution of the AE are exhausted, or the patient dies. The Investigator should use his/her discretion in ordering additional tests as necessary to monitor the resolution of such AEs.

#### 7.4.4 Discontinuation due to Adverse Event

Any patient who experiences an AE may be withdrawn at any time from the study at the discretion of the Investigator. For each patient withdrawn from the study due to an AE, whether serious or non-serious, the AE should be noted on the Adverse Events CRF and should be followed until the AE is resolved or stabilized, the condition becomes chronic in nature, all attempts to determine resolution of the AE are exhausted, or the patient dies. A decision to discontinue a patient due to an AE should be discussed with the Medical Monitor. If the AE may relate to overdose of study drug, the IB should be consulted for details regarding any specific actions to be taken.

#### 7.4.5 Pregnancy

Female patients must be instructed to discontinue all study drug and inform the Investigator immediately if they become pregnant during the study.

23 February 2021 CONFIDENTIAL Page 41 of 60

Protocol Number: TEN-02-402

Edition No. 2

The Investigator must report any pregnancy to InClin Safety within 1 business day of becoming aware of it. The patient must be immediately discontinued from further treatment with study drug. An uncomplicated pregnancy will not be considered an AE or SAE, but all pregnancies will be followed through birth.

Pregnancies are captured if they occur in female patients or in the sexual partners of male patients from the time the patient is first exposed to the study drug until 30 days after last exposure to the study drug.

Any congenital abnormalities in the offspring of a patient who received study drug will be reported as an SAE. The outcome of any pregnancy and the presence or absence of any congenital abnormality will be recorded in the source documentation and reported to InClin Safety.

#### 7.4.6 Serious Adverse Events

An SAE is any AE occurring from Screening through the end of the study, at any dose that results in any of the following outcomes:

- Death
- A life-threatening adverse drug experience
- Inpatient hospitalization or prolongation of existing hospitalization
- A persistent or significant disability/incapacity
- A congenital anomaly/birth defect

Important medical events that may not result in death, be life threatening, or require hospitalization may be considered an SAE when, based upon appropriate medical judgment, they may jeopardize the patient and may require medical or surgical intervention to prevent any of the outcomes listed in this definition. Examples of such medical events include allergic bronchospasm requiring intensive treatment in an emergency room or at home, blood dyscrasias or convulsions that do not result in inpatient hospitalization, or the development of drug dependency or drug abuse.

Note: SAEs require immediate reporting to InClin Safety. See "Reporting Serious Adverse Events" below for details.

23 February 2021 CONFIDENTIAL Page 42 of 60

Protocol Number: TEN-02-402

Edition No. 2

## 7.4.7 Reporting Serious Adverse Events

In the event of any SAE reported or observed during the study, whether or not attributable to the study drug, site personnel will report it to InClin Drug Safety within 24 hours of the knowledge of the occurrence.

To report an SAE, complete the study specific Serious Adverse Event Report Form and email

The SAE information will be entered into the EDC system and the AE will marked as "serious". This will trigger an email notification alert to the team that an SAE has occurred.

Reconciliation of SAE information in the EDC with the SAE information received and entered in the Argus database will be performed per the InClin Data Management Plan.

Safety Contact Information:

Investigator is required to submit SAE reports to the IRB/Independent Ethics Committee (IEC) in accordance with local requirements. All Investigators currently involved in clinical trials of tenapanor will receive safety alert notifications for submission to their local IRB/IEC as required. All reports sent to Investigators will blind the treatment assignment.

Follow-Up of SAE:

The Investigator must continue to follow the patient until the SAE has resolved or stabilizes (in the case of persistent impairment), the condition becomes chronic in nature, all attempts to determine resolution of the event are exhausted, or the patient dies.

#### 7.5 Efficacy Endpoints

Efficacy measures in this study include s-P (to be measured at all scheduled visits except Visit 2), iFGF23, PTH, medication dose, pill number, pill weight, and other information relative to drug usage (e.g., % on monotherapy), and patient experience.

The following efficacy endpoints will be analyzed by cohort and for the entire FAS at each post-baseline visit (only for s-P endpoints), the endpoint visit of the Treatment Period, and the endpoint visit of the entire study:

23 February 2021 CONFIDENTIAL Page 43 of 60

Protocol Number: TEN-02-402

Edition No. 2

- s-P response: achieving or maintaining s-P  $\leq$  5.5 mg/dL
- Normal s-P response: achieving s-P ≤4.5 mg/dL
- Borderline s-P response: achieving or maintaining s-P ≤6.5 mg/dL
- Change from baseline in s-P
- Relative change from baseline in iFGF23, derived as "change from baseline in iFGF23/baseline iFGF23"
- Change from baseline in PTH
- Change from baseline in total daily dose of PTH-modifying medications (mg)

The following efficacy endpoints will also be analyzed by cohort and for the entire "FAS (Cohorts 1-2)" at each post-baseline visit, the endpoint visit of the Treatment Period, and the endpoint visit of the entire study:

- Change from baseline in total daily dose of phosphorus-lowering medication (mg) (tenapanor and phosphate binder combined)
- Change from baseline in total daily pill weight (tenapanor and phosphate binder combined)
- Change from baseline in total daily pill number (tenapanor and phosphate binder combined)
- Medication dose response: achieving at least 30% reduction from baseline in total daily dose (mg) of phosphorus-lowering medication
- Pill weight response: achieving at least 30% reduction from baseline in total daily pill weight
- Pill number response: achieving at least 30% reduction from baseline in total daily pill number (e.g., reduce from 6 pills at baseline to ≤4 pills and reduce from 9 pills at baseline to ≤6 pills)
- Pill burden response: achieving pill weight response and pill number response
- s-P and medication dose response: achieving s-P response and medication dose response
- s-P and pill weight response: achieving s-P response and pill weight response
- s-P and pill number response: achieving s-P response and pill number response
- s-P and pill burden response: achieving s-P response, pill weight response, and pill number response
- Normal s-P and medication dose response: achieving normal s-P response and medication dose response
- Normal s-P and pill weight response: achieving normal s-P response and pill weight

23 February 2021 CONFIDENTIAL Page 44 of 60

Protocol Number: TEN-02-402

Edition No. 2

response

- Normal s-P and pill number response: achieving normal s-P response and pill number response
- Normal s-P and pill burden response: achieving normal s-P response, pill weight response, and pill number response
- Borderline s-P and medication dose response: achieving borderline s-P response and medication dose response
- Borderline s-P and pill weight response: achieving borderline s-P response and pill weight response
- Borderline s-P and pill number response: achieving borderline s-P response and pill number response
- Borderline s-P and pill burden response: achieving borderline s-P response, pill weight response, and pill number response

The final list of efficacy endpoints will be provided in the statistical analysis plan (SAP).

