#### **Efficacy Analyses:**

All efficacy measures will be summarized descriptively by cohort and for the entire FAS.

The following efficacy endpoints will be summarized descriptively by cohort and for the entire FAS at each post-baseline visit (only for s-P endpoints), the endpoint visit of the Treatment Period, and the endpoint visit of the entire study:

- s-P response: achieving or maintaining s-P ≤5.5 mg/dL
- Normal s-P response: achieving s-P ≤4.5 mg/dL
- Borderline s-P response: achieving or maintaining s-P ≤6.5 mg/dL
- Change from baseline in s-P
- Relative change from baseline in iFGF23, derived as "change from baseline in iFGF23/baseline iFGF23"
- Change from baseline in PTH
- Change from baseline in total daily dose of PTH-modifying medications (mg)

The following efficacy endpoints will also be summarized descriptively

Protocol Number: TEN-02-402

Edition No. 2

by cohort and for the entire "FAS (Cohorts 1-2)" at each post-baseline visit, the endpoint visit of the Treatment Period, and the endpoint visit of the entire study for patients switching their phosphate binder therapy to tenapanor therapy:

- Change from baseline in total daily dose of phosphorus-lowering medication (mg) (tenapanor and phosphate binder combined)
- Change from baseline in total daily pill weight (tenapanor and phosphate binder combined)
- Change from baseline in total daily pill number (tenapanor and phosphate binder combined)
- Medication dose response: achieving at least 30% reduction from baseline in total daily dose (mg) of phosphorus-lowering medication
- Pill weight response: achieving at least 30% reduction from baseline in total daily pill weight
- Pill number response: achieving at least 30% reduction from baseline in total daily pill number (e.g., reduce from 6 pills at baseline to ≤4 pills and reduce from 9 pills at baseline to ≤6 pills)
- Pill burden response: achieving pill weight response and pill number response
- s-P and medication dose response: achieving s-P response and medication dose response
- s-P and pill weight response: achieving s-P response and pill weight response
- s-P and pill number response: achieving s-P response and pill number response
- s-P and pill burden response: achieving s-P response, pill weight response, and pill number response
- Normal s-P and medication dose response: achieving normal s-P response and medication dose response
- Normal s-P and pill weight response: achieving normal s-P response and pill weight response

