## 4 STUDY DESIGN

## 4.1 Design Summary

This is a randomized, open-label study to evaluate different methods of initiating tenapanor therapy in CKD patients on dialysis with hyperphosphatemia, when they are either phosphate binder naïve or on phosphate binder therapy. The study consists of a Screening visit, a 10-week open-label Treatment Period (Part A), and an optional 16-week open-label Extension Period (Part B), with a total of three cohorts of patients as shown in Figure 4-1:

• Patients with s-P >5.5 and ≤10.0 mg/dL under stable phosphate binder treatment regimen are randomized in a 1:1 ratio to two different treatment cohorts:

[figure not shown]
23 February 2021 CONFIDENTIAL Page 24 of 60

Protocol Number: TEN-02-402

Edition No. 2

- Cohort 1 (straight switch), which stops taking phosphate binders and is immediately started on tenapanor 30 mg twice daily (BID) at Visit 2 (Day 1);
- Ochort 2, which decreases phosphate binder dose by at least 50% (may be more than 50% if patient is taking an odd number of binder pills each day), with ability to switch the binder regimen from thrice daily (TID) to BID or QD; and initiates tenapanor 30 mg BID at Visit 2 (Day 1).
- Phosphate binder naïve patients with s-P >4.5 and ≤10.0 mg/dL are enrolled as Cohort 3 and receive tenapanor at Visit 2 (Day 1) with a starting dose of 30 mg BID.

Figure 4-1: Study Design Diagram

a Day 1 is the randomization/enrollment day and serves as the reference day for all visits.

The Screening visit (Visit 1) must be scheduled at the first short dialysis interval of the week (Wednesday or Thursday), the Randomization/Enrollment visit (Visit 2) must be scheduled two days after the Screening visit at the second short dialysis interval of the week (Friday or Saturday), and all other visits in the study must be scheduled after a short dialysis interval (Wednesday or Friday for patients on a Monday-Wednesday-Friday schedule and Thursday or Saturday for patients on a Tuesday-Thursday-Saturday schedule). Body weight, vital signs, and blood collections for laboratory assessments must be performed pre-dialysis (prior to dialysis at the visit). All other assessments may be performed pre-, during, or post-dialysis but should be performed at the same time at each visit and the same day as dialysis.

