#### 9.4.6 Visit Windows

No analysis visit windows will be formally defined. The schedule of assessments and procedures in Section 1.3 details the intended collection of study variables at specified visits. Data collected at a scheduled visit will be used as the data at the corresponding analysis visit even if the visit is out-of-window. To minimize the amount of missing data, data collected at an unscheduled visit will be mapped to an analysis visit based on analysis windows if data at the corresponding scheduled visit are not available. Similarly, data from the Early Termination visit may also be mapped. Detailed information on analysis windows will be provided in the SAP.

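### Pill-number and pill-burden response do not require the patient to be on tenapanor, so a Cohort 2 patient with few baseline pills can become a responder by stopping it

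*Combined protocol and SAP*

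**What the plan says.** Section 7.5, repeated in Synopsis 1.2 (Efficacy Analyses), sets four single response endpoints for Cohorts 1 and 2: medication dose, pill weight, pill number and pill burden.

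- Pill number: "Pill number response: achieving at least 30% reduction from baseline in total daily pill number", with the examples "e.g., reduce from 6 pills at baseline to ≤4 pills and reduce from 9 pills at baseline to ≤6 pills".
- Pill weight: "Pill weight response: achieving at least 30% reduction from baseline in total daily pill weight".
- Pill burden: "Pill burden response: achieving pill weight response and pill number response".
- The count covers both drugs, as the matching change endpoint shows: "Change from baseline in total daily pill number (tenapanor and phosphate binder combined").

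Twelve composites join each of the four responses to one of three s-P thresholds. All are reported at every post-baseline visit and at the endpoint visits of the Treatment Period and the study. None carries a condition on tenapanor use.

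Other sections decide which observations enter:

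- 4.1: at Day 1 Cohort 2 starts tenapanor and "decreases phosphate binder dose by at least 50" per cent.
- 7.4.1: action on study drug after an adverse event is coded as "dose not changed, dose reduced, drug interrupted, drug withdrawn, or not applicable". Leaving the study is a separate item.
- 9.3: the FAS needs eligibility, one dose and one later s-P value.
- 9.4.4: descriptive summaries use observed data without imputation, so there is no non-responder rule.
- 9.4.6: "data from the Early Termination visit may also be mapped" to an analysis visit.
- 7.5 and 9.1: the final endpoint list is left to a separate SAP, which governs where it differs.

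**The concern.** The secondary objective in 3.2 is the effect of tenapanor on reducing pill burden. The response rule counts tenapanor tablets as burden but never asks whether the patient still takes them. Stopping the drug therefore removes two tablets a day from the count, and a patient who gave up because of intolerance can be scored as a success of the strategy.

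At the starting regimens the reclassification arises in Cohort 2 and not in Cohort 1, so it would also disturb any exploratory comparison between the two randomised cohorts.

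**Working it through.** **Inputs.** Response means a reduction of at least 30% in total daily pills (7.5). Tenapanor is one tablet twice daily, so 2 tablets (2.2; starting dose in 6.1.3). Minimum baseline binder pills are 6 a day for Renvela, Auryxia or PhosLo and 3 a day for Fosrenol or Velphoro (5.1, criterion 6). Cohort 2 binder pills are taken as floor(B/2), where B is the baseline count. Rounding down is an assumption, consistent with the remark in 4.1 that odd counts may be cut by more than half.

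**The plan's own cut-offs.** The largest count that still responds is the integer part of 0.7 × B. For B = 6, 0.7 × 6 = 4.2, giving 4. For B = 9, 0.7 × 9 = 6.3, giving 6. Both match 7.5.

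**Cohort 2, binder halved.** On drug the reduction is (B − floor(B/2) − 2)/B. Off drug it is (B − floor(B/2))/B.

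| B | Pills on drug | Reduction | Response | Pills off drug | Reduction | Response |
|---|---|---|---|---|---|---|
| 3 | 3 | 0% | no | 1 | 66.7% | yes |
| 4 | 4 | 0% | no | 2 | 50.0% | yes |
| 5 | 4 | 20.0% | no | 2 | 60.0% | yes |
| 6 | 5 | 16.7% | no | 3 | 50.0% | yes |
| 7 | 5 | 28.6% | no | 3 | 57.1% | yes |
| 8 | 6 | 25.0% | no | 4 | 50.0% | yes |
| 9 | 6 | 33.3% | yes | 4 | 55.6% | yes |
| 10 | 7 | 30.0% | yes | 5 | 50.0% | yes |
| 12 | 8 | 33.3% | yes | 6 | 50.0% | yes |

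Every count from 3 to 8 switches, including both eligibility minimums. From 9 upward a switch needs binder to have been added back. With B = 12 and 7 binder pills, the reduction is (12 − 9)/12 = 25% on drug and (12 − 7)/12 = 41.7% off.

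**How long the binder must stay reduced.** At B = 6 off drug, up to 4 binder pills still counts as response; a return to 6 does not. The general rule in 6.1.4 bars binder increases until Visit 4, so at Visit 3 a patient following the protocol still has the reduced binder.

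**Cohort 1.** With 2 tenapanor tablets and no binder, the reduction is (3 − 2)/3 = 33.3% at B = 3 and (6 − 2)/6 = 66.7% at B = 6. The patient already responds at every eligible count, so stopping (0 pills, 100%) changes no pill-number classification. A patient who stopped for intolerance and takes no binder is nevertheless still counted as a success.

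**Pill burden.** With tenapanor stopped and the binder halved, pill weight falls by about 50%. Weight response is met, and pill burden switches with pill number.

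**Pill weight alone.** For a tenapanor tablet of weight w and a binder pill of weight W, the on-drug reduction is 0.5 − 2w/(B × W). It falls below 30% only if w/W exceeds 0.1 × B, which is 0.6 at B = 6 and 0.8 at B = 8. The documents give no tablet weights.

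**Medication dose.** On drug, D/2 + 60 ≤ 0.7 × D holds when D ≥ 60/0.2 = 300 mg. With the binder halved, a switch needs a baseline total below 300 mg.

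**Size.** The documents give neither a baseline pill distribution nor an off-drug rate, so the following figures are assumptions.

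- Suppose 25 to 75% of Cohort 2 have 8 or fewer pills and keep the binder halved, and 5 to 30% of them are off tenapanor at a visit. The present rule then adds 0.25 × 0.05 = 1.25 points (1.9 of 150) up to 0.75 × 0.30 = 22.5 points (33.8 of 150), compared with the same patients staying on drug.
- Binder add-back works the other way. Suppose 40% of patients on drug respond, 10% are off drug, and a fraction r of those off drug respond. The rate is 0.40 × 0.90 + 0.10 × r. This is 46% at r = 1, 41% at r = 0.5 and 36% at r = 0, the last being below the 40% seen on drug.

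**The case against.** The strongest reply is that the protocol is not the last word. Section 9.1 makes a separate SAP govern, 7.5 leaves it the final endpoint list, and 9.4.6 leaves it the analysis windows. A rule for patients off tenapanor could sit there. This stands as a limit, but the endpoint wording in the protocol contains no such rule.

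Second, these are secondary endpoints summarised descriptively; any testing is exploratory (9.4.3), and the sample size has no statistical basis (9.2). That stands and bears on priority.

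Third, binder can be added from Visit 4 when s-P exceeds 5.5 mg/dL (6.1.4), and 2.4 says existing binder treatment continues once participation ends. Both can turn an off-drug patient back into a non-responder. The s-P composites filter further, although an s-P drawn soon after stopping can still meet its threshold.

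Fourth, the supporting passages should not be over-read. The list in 7.4.1 is a generic set of codes for tenapanor or binder and does not show that the sponsor expects many withdrawals. Early Termination means leaving the study, not being off drug: drug return is part of that visit, so some patients may have been dosing until then. The protocol also does not say whether pills are counted as prescribed or as taken; a brief interruption matters only if they are counted as taken.

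Finally, restricting the change endpoints to patients on tenapanor would condition on something that happens after randomisation. That objection is sound, and the fix below respects it.

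**Conclusion.** The gap is real for pill-number and pill-burden response: two single endpoints and, partly filtered by s-P, their six composites. At the starting regimen it affects Cohort 2 patients with 3 to 8 baseline pills whose binder is still reduced; at higher counts it needs binder to have been added back. This rests on two tenapanor tablets a day and a binder count rounded down to half.

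A reader might infer three stronger things that the documents do not support:

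- **That all four responses are inflated.** No switch is shown for pill weight alone, because tablet weights are not given. For mg dose with the binder halved, it needs a baseline total below 300 mg.
- **That stopping tenapanor raises response rates in general.** Cohort 1 on tenapanor alone already responds on pill number, and restoring binder can lower the Cohort 2 rate.
- **That a particular inflation can be quoted.** The figures above are illustrations on assumed inputs.

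The primary objective is untouched. The definition should still be corrected, because applied literally it can credit abandoning the drug as success against the pill-burden objective.

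**What to change.** In 7.5, Synopsis 1.2 and the SAP, add to the dose, pill-weight, pill-number and pill-burden responses, single and composite: *and receiving tenapanor (currently prescribed and not interrupted or withdrawn) at that visit*. Count off-tenapanor visits as non-response, including Early Termination visits after tenapanor was stopped. Keep the present definition as a sensitivity analysis. Applying the condition to all four responses keeps them consistent, even though a switch is shown for only two.

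For the three change endpoints, keep all observed values as the main summary. Report the number off tenapanor at each visit by cohort, and show the on-tenapanor summary only as supplementary. State in the SAP whether pills are counted as prescribed or as taken.

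The cost is wording and programming. Dispensing, return and adverse-event action data are already collected, and the endpoints themselves need the daily tenapanor tablets at each visit. Adverse-event action codes alone would miss stopping for other reasons, so status should not rest on them alone. No visit or treatment changes. The downside is that response rates become somewhat lower.
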